7.5 Analysis of Safety

Safety analyses will be performed using the Safety Analysis Set (SAF).

Missing dates' imputation rules for AE onset date and stop date are detailed in Section [7.11.2](#)

For each safety parameter, the last non-missing assessment prior to the first dose of study drug will be used as the baseline for all analyses, unless specified otherwise.

7.5.1 Adverse Events

All adverse events will be coded using the Medical Dictionary for Regulatory Activities (MedDRA) version 20.0. They will be summarized by System Organ Class (SOC) and Preferred Term (PT).

7.5.1.1 Overview

An overview table will include the following details, by treatment arm:

- Number and percentage of subjects with TEAEs,
- Number and percentage of subjects with causally drug related TEAEs,
- Number and percentage of subjects with serious TEAEs,
- Number and percentage of subjects with serious drug related TEAEs,
- Number and percentage of subjects with TEAEs leading to permanent discontinuation of study drug,
- Number and percentage of subjects with causally drug related TEAEs leading to permanent discontinuation of study drug,
- Number and percentage of subjects with NCI CTC Grade 3 or higher TEAEs,
- Number and percentage of subjects with TEAEs leading to death
- Number and percentage of subjects with drug related TEAEs leading to death and
- Number of deaths occurring during the Safety Emergent Period and overall.

7.5.1.2 Proportion of subjects with TEAEs by SOC/PT

The number and percentage of subjects with TEAEs, as classified by SOC and PT will be summarized by treatment arm. Summaries will be provided for:

- TEAEs
- TEAEs (by PT only)
- Drug related TEAEs,
- TEAEs with NCI CTC Grade 3 or higher
- TEAEs by severity

- Drug related TEAEs by severity
- Serious TEAEs,
- Drug related serious TEAEs,
- TEAEs leading to permanent discontinuation of study drug,
- Drug related TEAEs leading to permanent discontinuation of study drug,
- TEAEs excluding serious adverse events that equal to or exceed a threshold of 5.0% in any treatment arm (roxadustat or placebo),
- TEAEs leading to death,
- Drug-related TEAEs leading to death,
- Common TEAEs that equal to or exceed a threshold of 5.0% in any treatment arm (roxadustat or placebo)
- TEAEs by relationship to the study drug,
- AEs occurring during the post study follow up period
- Serious AEs during the post-study follow up period
- Onset of common ($\geq 5\%$ in Any treatment arm(roxadustat or placebo)) TEAEs by treatment duration: <3 months, ≥ 3 to ≤ 6 months, >6 to ≤ 12 months, >12 months

For the summaries by severity or relationship to the study drug, in the subject count, if a subject has multiple TEAEs with the same SOC or PT, but with different severity or relationship, then the subject will be counted only once with the worst severity and highest degree of relationship, however, if any of the severity or relationship values are missing then the subject will be counted only once with missing severity or relationship. In the adverse event count, the adverse events will be presented in each category they were classified to. Drug related TEAEs will be presented in a similar way by severity only.

Maximum severity or relationship will be defined as the worst severity and highest degree of relationship on-treatment (see Section 6.2).

No queries will be done for SMQs.

7.5.1.3 Event-rates per 100 patient-years

The number of events and event rate (per 100 patient years) during the Safety Emergent Period with TEAEs, as classified by SOC and PT will be calculated by treatment arm. Summaries will be provided for:

- TEAEs
- TEAEs censored at start of chronic dialysis
- TEAE NCI CTC Grades 3 or higher
- Serious TEAEs,
- TEAEs leading to death.

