6.2.1.3 Time to occurrence of a TEAE (by type of AE group)

TEAEs are also classified into a number of groups depending on the following factors:

- Serious TEAEs
- Death during the Safety Emergent Period
- Any deaths (during the 24-month period)
- Related Serious TEAEs
- TEAEs Leading to permanent Discontinuation of the study drug
- TEAEs NCI CTC Grade 3 or Higher
- MedDRA System Organ Class (SOC)

The time to occurrence for a subject with a TEAE for a given type (except any deaths) will be calculated (in years) as:

$(\text{First TEAE date of the given type during the Safety Emergent Period} - \text{Analysis date of first dose intake} + 1) / 365.25$

With 'Analysis date of first dose intake' defined in Section [6.5.4](#) All adverse events collected during the Safety Emergent Period will be counted as TEAE, irrespective of use of rescue therapy.

Subjects who have not experienced a TEAE for that given type will be censored; the subject will be censored and the time to censoring for these subjects will be calculated (in years) as:

$(\text{Date of End of Safety Emergent Period} - \text{Analysis date of first dose intake} + 1) / 365.25$

With date of end of Safety Emergent Period defined in Section [7.11.5](#)

For any deaths during the 24-month period (including those occurring during the Post-Study Follow Up Period), time to occurrence for a subject who died during study / post study follow up) will be calculated (in years) as:

$[\text{End date for corresponding Fatal AE} - \text{Analysis date of first dose intake} + 1] / 365.25$

With 'End date for corresponding Fatal AE' which cover both study and post-study FU occurring up to Day 760 (i.e., month 24 + one month follow up + 3 days window as per protocol).

Subjects who have not died; the subject will be censored and the time to censoring for these subjects will be calculated (in years) as:

$\text{Minimum between } [\text{Day 760 and Max (Date of last known date when subject alive (End of Post-study FU), Date of last contact (Post study FU visit/call), Date of last Study evaluation (EOS form))} - \text{Analysis date of first dose intake} + 1] / 365.25$

Additional analyses censoring data post dialysis:

Time to occurrence with censoring all data at the initiation of permanent dialysis will be calculated as above where events occurring after initiation of dialysis will not be considered.

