Subjects who initiated dialysis and who have not experienced an event prior to the dialysis will be censored and the time to censoring for these subjects will be calculated (in years) as:

$$(\text{Date of first dialysis} - \text{Analysis date of first dose intake} + 1) / 365.25$$

Subjects who have not experienced an event and did not initiate dialysis during the Safety Emergent Period, the time to censoring will be calculated (in years) as

$$(\text{Date of End of Safety Emergent Period} - \text{Analysis date of first dose intake} + 1) / 365.25.$$

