6.2.1.6 Definitions of event rate

The event rate (per 100 patient year) during the Safety Emergent Period will be calculated as either:

$$\frac{\text{Number of events}}{\text{Patient Exposure Years}} \times 100$$

Or

$$\frac{\text{Number of subjects experiencing an event}}{\text{Patient Exposure Years}} \times 100$$

Where Patient Exposure Years is defined as [Sum of individual exposure in days (Analysis date of last dose – Analysis date of first dose + 1)] / [(Duration of Safety Emergent Period in days / 365.25)].

The definition used will be indicated in the description of the corresponding analysis in Section [7](#)

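### The event rate for TEAEs censored at chronic dialysis has no denominator that stops at dialysis, so events are cut off but exposure is not

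*SAP*

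**What the plan says.** SAP 7.5.1.3 (Event-rates per 100 patient-years) lists five summaries by SOC and PT. One is all TEAEs; the next is "TEAEs censored at start of chronic dialysis". No denominator is given for either row, and no other section is cited for the dialysis row.

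SAP 6.2.1.6 (Definitions of event rate) opens with "The event rate (per 100 patient year) during the Safety Emergent Period will be calculated as either" and offers two numerators, a count of events or a count of subjects. Both go over the same denominator, Patient Exposure Years, defined as "Sum of individual exposure in days (Analysis date of last dose – Analysis date of first dose + 1", with that sum then divided by "Duration of Safety Emergent Period in days / 365.25". Dialysis is not mentioned. The section adds "The definition used will be indicated in the description of the corresponding analysis in Section" 7, but 7.5.1.3 names no other exposure measure.

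SAP 6.2.1.3 does contain a dialysis rule, written for time to occurrence, and it has two halves. On events: "where events occurring after initiation of dialysis will not be considered". On time: "Subjects who initiated dialysis and who have not experienced an event prior to the dialysis will be censored", with the clock ending at dialysis. Section 6.2.1.5 carries this into the incidence rate, whose denominator sums time to event or to censoring, and 7.5.1.5 cites 6.2.1.3 when it asks for the dialysis-censored incidence rates.

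Protocol Appendix 4 allows subjects who start temporary or permanent dialysis to remain in the study and continue study drug. Exposure after dialysis is therefore expected.

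**The concern.** A rate needs its events and its time counted over the same span. In the dialysis-censored row the numerator stops at chronic dialysis, while the only denominator available runs to last dose. Time on drug after dialysis then counts as if it were event-free.

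Two uses of the row suffer. The SAP's revision history (Section 8, version 2.0, item 11) says that censoring at dialysis is there to assess its impact on AE incidence. Version 3.0, item 23 says that event rates were added so that arms with different exposure could be compared fairly. A rate with mismatched spans serves neither purpose: it moves with the amount of on-drug dialysis time in an arm as well as with the AE burden before dialysis.

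**Working it through.** The documents state no event rate, exposure total or dialysis share, so there is no figure of the plan's own to reproduce. All shares, durations and rates below are assumptions.

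**1. Against a last-dose exposure denominator.** Let T be an arm's exposure in years from first to last dose (6.2.1.6, read as person-years), f the share of T after chronic dialysis starts, and E the events before dialysis.

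- Rate as written: 100 E / T
- Rate with exposure stopped at dialysis: 100 E / [T(1 − f)]
- Ratio: 1 − f

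With an assumed pre-dialysis rate of 200 per 100 patient-years:

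| f | Rate as written (200 × (1 − f)) | Shortfall |
|---|---|---|
| 5% | 190 | 5% |
| 10% | 180 | 10% |
| 20% | 160 | 20% |

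If f differs by arm, the ratio of roxadustat to placebo rates is multiplied by (1 − f_R)/(1 − f_P):

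- 5% versus 10%: 0.95/0.90 = 1.056
- 10% versus 5%: 0.90/0.95 = 0.947
- 12% versus 8%: 0.88/0.92 = 0.957

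**2. Against pre-dialysis Safety Emergent time.** Events count to 28 days after last dose (SAP 6.2), but exposure ends at last dose, which pushes the rate up. Let D be mean exposure in days and p the share of subjects starting chronic dialysis. With a constant event rate and the 28-day tail counted only for subjects without dialysis:

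- Rate as written / rate on Safety Emergent time before dialysis = (1 − f) + (1 − p) × 28/D

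| D | p | f | Calculation | Ratio |
|---|---|---|---|---|
| 364 | 5% | 1.25% | 0.9875 + 0.95 × 28/364 | 1.06 |
| 546 | 10% | 5% | 0.95 + 0.90 × 28/546 | 0.996 |
| 728 | 30% | 15% | 0.85 + 0.70 × 28/728 | 0.88 |

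The two effects can cancel, or either can dominate.

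**3. Censored row against uncensored row.** Under 6.2.1.6 both rows share one denominator within an arm, so it cancels:

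- Censored rate / uncensored rate = E_pre / E_all ≤ 1

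This holds whatever the denominator is and whether or not the 28-day tail is counted. Now leave the tail aside and let r_pre and r_post be the event rates on exposure before and after dialysis:

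- As written: (1 − f) r_pre / [(1 − f) r_pre + f r_post]
- With exposure stopped at dialysis: r_pre / [(1 − f) r_pre + f r_post]

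If r_post = r_pre, the second ratio is 1, correctly showing no effect of dialysis, while the first is 1 − f. If r_post is below r_pre, the second exceeds 1; the first is still below 1 whenever any event follows dialysis.

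**4. The printed formula.** Dividing summed exposure by the Safety Emergent Period duration in years does not give person-years. For 300 subjects with 546 days each and a Safety Emergent Period of 546 + 28 = 574 days:

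- Plain person-years: 300 × 546 / 365.25 = 448
- As printed, durations summed over subjects: 300 × 546 / (300 × 574 / 365.25) = 347
- As printed, mean duration: 300 × 546 / (574 / 365.25) = 104,230

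This is a separate defect in the same definition. Repairing it alone leaves the dialysis mismatch in place.

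**The case against.** The strongest reply is that the SAP never says full exposure is kept for this row. Censoring is a follow-up-time term in this SAP, the rule in 6.2.1.3 has a time half as well as an event half, and a programmer might apply both. That is fair as far as it goes: full exposure is the default of 6.2.1.6 and is not stated for the row. But 7.5.1.3 cites neither half of 6.2.1.3, that rule is written for time to occurrence, and 7.5.1.5 does cite it when it is meant to apply. The sentence in 6.2.1.6 that defers to Section 7 does not help either, since both rate forms share one denominator. Someone following the text divides by exposure to last dose.

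The second reply concerns direction and size. A reader might infer that the rate is simply too low by f. The documents do not support that without qualification: it is exact only relative to exposure to last dose, and the 28-day event tail acts the other way. This reply stands.

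The third concerns importance. 7.5.1.3 plans no test, confidence interval or rate ratio, so the between-arm multipliers above distort no planned statistic, only a reader's own comparison. The dialysis-censored incidence rates in 7.5.1.5, including those by SOC and common PT, stop time properly. This also stands. Those are first-event rates, however, and the row in 7.5.1.3 is the dialysis-censored summary of all events.

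**Conclusion.** The gap is real. SAP 6.2.1.6 supplies one event-rate denominator with no stop at dialysis, 7.5.1.3 uses it for a row whose events stop at dialysis, and dosing may continue on dialysis. Applied as written, the row is (1 − f) times the rate on pre-dialysis exposure: 5% to 20% low for an assumed f of 5% to 20%. Against pre-dialysis Safety Emergent time, the ratio ran from about 1.06 to 0.88 over assumed mean exposures of 52 to 104 weeks and 5% to 30% of subjects starting dialysis. The finding that needs no assumed figure is that the censored row can never exceed the uncensored row, so comparing them cannot show the effect of dialysis.

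The consequence is confined to one descriptive table. A reader might go further and conclude that the trial's dialysis-censored safety analyses are biased in general. The documents do not support this, because the incidence rates and hazard ratios in 7.5.1.5 follow 6.2.1.3 and end time at dialysis.

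**What to change.** In SAP 6.2.1.6 and 7.5.1.3, state that for the row censored at chronic dialysis each subject's exposure runs from first dose to the earlier of (a) the date of first chronic dialysis and (b) the end point used for every other row in 7.5.1.3, and that only events starting before the dialysis date are counted. The common end point matters: if this row alone ran to the end of the Safety Emergent Period, the censored and uncensored rows would again differ for a reason unrelated to dialysis.

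At the same time, correct Patient Exposure Years to plain person-years, that is, summed days divided by 365.25.

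The cost is a sentence in the SAP, one derived exposure variable and a corrected formula. No new data are needed.

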7.5.1.4 Incidence rates and cumulative incidence

Since the percentage of adverse events might be different between treatment arms due to the difference in the discontinuation rates, in addition to the frequency tables above, the incidence rate (per 100 subject years at risk) and the cumulative incidence at 6 months, 12,

18 months & 24 months with the 95% confidence interval, using Greenwood's formula, will be reported by treatment arm.

It will be done for each of the following event types of special interest:

- Serious TEAEs,
- TEAE for each SOC (>10% for a SOC in total SAF)
- Deaths occurring during the Safety Emergent Period,
- Any death (including post-study follow up period),
- Related serious TEAEs,
- AEs leading to discontinuation of study drug, and
- TEAE NCI CTC Grades 3 or higher.

Hazard ratios of each of the TEAE categories of special interest above will be computed by using Cox Proportional Hazards regression stratified on region and history of CV and adjusted on baseline Hb and baseline eGFR as continuous covariates. Hazard ratios (roxadustat as relative to placebo) and their 95% CI will be calculated for each TEAE category.

As a sensitivity analysis, the above analysis will be repeated using IPCW method (Appendix 10.7) for the following event types of special interest:

- Serious TEAEs,
- TEAE for each SOC (>10% for a SOC in total SAF)
- Deaths occurring during the Safety Emergent Period, and
- TEAE NCI CTC Grades 3 or higher.

A dot-and-forest plot will be produced showing each of the above TEAE categories on the y-axis. The incidence rates by treatment arm, the stratified Cox hazard ratios (roxadustat as relative to placebo) and their 95% CI will be shown on the x-axis.

In addition, cumulative incidence plots for subjects experiencing each of the TEAE categories above will be produced by treatment arm.

Incidence rate (per 100 subject years at risk) in each treatment arm by SOC and PT and the cumulative incidences by SOC will also be produced for the most common TEAEs ($\geq 5\%$ in total SAF). In addition, cumulative incidence plots of subjects experiencing at least one most common TEAEs in a SOC will be produced. A dot-and-forest plot will be produced showing each SOC in the y-axis and the incidence rates, the Cox hazard ratio and its 95% CI in the x-axis. The SOC will be sorted by the hazard ratio.

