7.2.1 Disposition of Subjects

The following subject data will be summarized and presented:

- Number and percentage of subjects with informed consent, who discontinued before randomization and randomized (overall only);

- Number and percentage of subjects randomized in each analysis set, by treatment arm and overall;
- Number and percentage of subjects who completed and discontinued treatment in each period (primary treatment period and extended treatment period), by primary reason for treatment discontinuation and by treatment arm for All Randomized, SAF, FAS and PPS;
- Number and percentage of subjects who completed and discontinued the study, by primary reason for study discontinuation and by treatment arm for All Randomized and SAF;
- Number and percentage of subjects who completed and discontinued the post study follow-up period for All Randomized and SAF, and
- Number and percentage of subjects excluded from PPS by reason for exclusion defined in Section 5.3 by treatment arm for the FAS.

The following data will be presented graphically by treatment arm for the FAS and the SAF:

- Treatment discontinuation by reason using bar chart;
- Treatment discontinuation by time interval and reason using bar chart; and
- Time to treatment discontinuation using a Kaplan-Meier plot.

In addition, the following graphs will be done by treatment arm, for the FAS and PPS:

- Treatment discontinuation for lack of efficacy using a cumulative incidence plot;
- Treatment discontinuation for adverse event using a cumulative incidence plot.
- Treatment discontinuation for withdrawal by subject using a cumulative incidence plot.

Time intervals will be analyzed using the following categories:

- Less than 2 weeks
- At least 2 weeks, less than 4 weeks
- At least 4 weeks, less than 12 weeks
- At least 12 weeks, less than 24 weeks
- At least 24 weeks, less than 36 weeks
- At least 36 weeks, less than 52 weeks
- At least 52 weeks, less than 78 weeks
- 78 weeks or more
- Unknown.

In addition, the randomization stratification strata from both sources (CRF and IRT) will be reported by treatment arm. Discrepancy between stratification from CRF and IRT will be summarized and the total number of patients with discrepancy overall and for each stratification factor will be provided

Subjects who screened failure will also be listed.

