The cumulative incidence will be calculated as one minus the Kaplan-Meier estimate of the survival function. Two types of analyses can be performed: modeling the cause specific hazard or modeling the hazard of the sub-distribution. The first approach has been chosen in this SAP, because competing risks are assumed not to exist, since the main interest is to study the treatments effect and this method provides results to be generalized across datasets with different competing risks. One minus the Kaplan-Meier estimate can be interpreted as the probability that an event of interest occurs to a subject by time t, in the absence of any competing risk.

In addition to the cumulative incidence plot, the cumulative incidence at 3, 6 and 9 months with the 95% confidence interval will be reported using Greenwood's formula.

Model checking

The proportional hazards assumption will be checked graphically using a log-cumulative hazard plot against log-survival time. This plot will give approximately parallel lines if the proportional hazards assumption between treatment arms subgroups holds. This plot will be provided as part of the raw SAS outputs.

In addition, the number and percentage of subjects with an increase from baseline in blood pressure during the Safety Emergen Period will be reported by treatment arm (roxadustat and placebo) on the PPS. For subjects who have experienced more than one increase in blood pressure, only their first event following study treatment will be used in the analysis.

In addition, the incidence rate (per 100 subject years at risk) will be calculated as follows:

$$\frac{\text{Number of subjects with event}}{\text{Total cumulative time at risk (years)}} \times 100$$

Where Total cumulative time at risk is the sum of individual time at risk defined as either time to occurrence of the event or time to censoring for subjects with no event.

Number of subjects at risk is defined as the number of subjects with (censored or non-censored) times to the event of interest greater or equal to t.

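### Cumulative incidence of AEs leading to discontinuation is set as one minus Kaplan-Meier with other-reason stops and deaths censored, which overstates the share of subjects who actually stop for an AE

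*SAP*

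**What the plan says.** - **What is reported.** SAP 7.5.1.4 gives incidence rates and cumulative incidence at 6, 12, 18 and 24 months: "18 months & 24 months with the 95% confidence interval, using Greenwood's formula, will be reported by treatment arm". The list of event types includes "AEs leading to discontinuation of study drug, and". SAP 7.5.1.5 repeats the cumulative incidence of this event by baseline eGFR category and with data censored at chronic dialysis.
- **Why it is reported.** 7.5.1.4 explains that AE percentages "might be different between treatment arms due to the difference in the discontinuation rates".
- **The estimator.** 7.5.1.4 does not define cumulative incidence. The definition is in 7.4.2.7, under the hypertension endpoint: "The cumulative incidence will be calculated as one minus the Kaplan-Meier estimate of the survival function". The reason given there covers the whole plan: "The first approach has been chosen in this SAP, because competing risks are assumed not to exist". The same section reads the result as the "probability that an event of interest occurs to a subject by time t, in the absence of any competing risk".
- **The censoring.** SAP 6.2.1.3 lists "TEAEs Leading to permanent Discontinuation of the study drug" as an event group and dates the event at the first such TEAE. Subjects without one are censored at the end of the Safety Emergent Period, whatever their reason for stopping. That period normally ends 28 days after last dose, or at death if earlier (6.2, 7.11.5).
- **Related displays.** SAP 7.2.1 plans three by-reason plots, for lack of efficacy, adverse event and withdrawal by subject, for example "Treatment discontinuation for lack of efficacy using a cumulative incidence plot". It names no estimator for them.

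**The concern.** For most AE categories one can argue about what censoring at the end of follow-up means. This event is different because it is itself one of the ways of stopping drug. A subject who has permanently stopped for withdrawal of consent, a third ESA course or a transplant (protocol 3.3), or who has died, cannot later stop because of an AE. Kaplan-Meier treats each of these subjects as someone who could still have the event and would have it at the rate seen in those still on drug. Competing events exist here by construction, so the stated premise of the method is false for this event.

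The consequence is a labelled 6- to 24-month figure, with a confidence interval, that exceeds the proportion of subjects who stop for an AE by that time. The excess depends on how much other-reason stopping there is. The section was added because discontinuation may differ between arms, and for this event that same difference makes the overstatement unequal.

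**Working it through.** The plan states no figure for this point, so there is none to reproduce.

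**Inputs from the documents:** 1-KM (SAP 7.4.2.7); censoring at last dose + 28 days (6.2, 7.11.5); planned treatment of 52 to 104 weeks.

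**Assumed, because the documents give no rates:** constant yearly hazards, *a* for stopping because of an AE and *b* for all other unplanned stops including death.

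**Formulas at time t, without the 28-day tail:**
- 1-KM = 1 - exp(-*a*t)
- Actual cumulative incidence (the Aalen-Johansen target) = *a*/(*a*+*b*) × [1 - exp(-(*a*+*b*)t)]

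**24 months, *a* = 0.06:**
- 1-KM = 1 - exp(-0.12) = 11.3%, whatever *b* is.
- *b* = 0.2: 0.06/0.26 × [1 - exp(-0.52)] = 9.4%, an excess of 2.0 points (ratio 1.21).
- *b* = 0.5: 0.06/0.56 × [1 - exp(-1.12)] = 7.2%, an excess of 4.1 points (ratio 1.57).
- Over *a* = 0.03-0.10 and *b* = 0.1-0.8 the excess runs from 0.5 to 8.9 points and is never negative.

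**Adding the SAP's tail.** Let L = 28/365.25 years and let G(t) be the share whose planned treatment end lies beyond t. The share still on drug is on(t) = exp(-(*a*+*b*)t) × G(t). Under the SAP's rule the risk set at t is R(t) = on(t-L) minus the AE stops between t-L and t. The Kaplan-Meier hazard is *a* × on(t)/R(t), and 1-KM is one minus the exponential of minus its integral. With planned ends uniform between weeks 52 and 104 and *a* = 0.06, the 18-month values are as follows (excess taken before rounding):

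| Other stops *b* (per year) | Actual | 1-KM, no tail | Excess | 1-KM, + 28 days | Excess |
|---|---|---|---|---|---|
| 0.20 | 7.5% | 8.6% | 1.2 | 8.2% | 0.8 |
| 0.25 | 7.2% | 8.6% | 1.4 | 8.2% | 1.0 |
| 0.40 | 6.5% | 8.6% | 2.1 | 8.1% | 1.6 |
| 0.50 | 6.1% | 8.6% | 2.5 | 8.1% | 2.0 |

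If half the subjects have the full 104 weeks and the rest are uniform between 52 and 104, the excess with the tail is 0.9-2.1 points. For that second pattern, a simulation at 24 months gave 10.9% against 9.4% (*b* = 0.2) and 10.8% against 7.3% (*b* = 0.5). The tail trims the excess but does not remove it.

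**Comparison between arms.** With equal *a*, the arm with more other-reason stopping is overstated more. Comparing *b* = 0.2 with *b* = 0.5, the relative overstatement stayed larger in the higher-drop-out arm throughout (about 1.56-1.57 against 1.18-1.21). In absolute points the order reversed only when the lower-drop-out arm's AE-stop hazard was about 2.5 to 3 times the other's.

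**The case against.** **It is a choice of estimand.** 7.4.2.7 weighs two approaches and states the hypothetical reading openly. With equal AE-stop hazards, 1-KM correctly shows equal curves. Aalen-Johansen would show the arm with less other-reason drop-out as worse only because its subjects stayed on drug longer. This is true, and it is why the cause-specific Cox hazard ratio should stay: it answers the question about hazards. But the plan does not defend a hypothetical quantity for this event. It assumes that competing risks do not exist, and here they do.

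**The actual counts are already planned.** 7.5.1.1 and 7.5.1.2 tabulate subjects with TEAEs leading to permanent discontinuation, and 7.2.1 gives discontinuation by primary reason and by time interval. So a reader who infers that 1-KM hides how many stopped for an AE goes further than the documents allow. What the tables lack is a correct figure at 6 to 24 months: planned treatment varies from 52 to 104 weeks, and crude percentages do not account for that.

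**The direction is not known.** It is tempting to infer that placebo subjects drop out more and that the method therefore flatters roxadustat. 7.5.1.4 speaks only of a difference, and Appendix 10.7 only of a possible one. Neither names an arm.

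**The definition is carried over.** 7.5.1.4 does not repeat 1-KM. The plan-wide wording in 7.4.2.7, the use of Greenwood's formula and the absence of any other estimator make the carry-over the natural reading. For the 7.2.1 plots it is weaker: that section distinguishes a Kaplan-Meier plot (overall discontinuation) from cumulative incidence plots (by reason). An error there cannot be asserted, only that the estimator is unstated.

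**IPCW might be thought to cover it.** The IPCW list in 7.5.1.4 omits this event type, and the method in Appendix 10.7 also targets the no-censoring quantity.

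**Conclusion.** The point holds for one event type, AEs leading to discontinuation, in SAP 7.5.1.4 and 7.5.1.5. Under the plan's rules 1-KM overstates the share of subjects who stop for an AE. At similar AE-stop hazards the overstatement is larger in whichever arm has more other-reason drop-out.

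The size rests entirely on assumed constant hazards. At 0.06/year for AE stops and 0.2-0.5/year for other stops, it is about 0.8-2.0 points at 18 months with the plan's own censoring, and 2.0-4.1 points at 24 months if the 28-day tail is ignored. The upward direction does not depend on those values.

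This is a descriptive safety display outside the fixed testing sequence, and no primary or key secondary conclusion depends on it. It should be corrected because the stated premise is wrong and the correction is cheap.

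**What to change.** - **7.5.1.4 and 7.5.1.5:** estimate the cumulative incidence of AEs leading to discontinuation by Aalen-Johansen, with unplanned discontinuation for any other reason and death as competing events. Planned end of treatment stays as censoring, as does dialysis start in the dialysis-censored version.
- **Classification:** state one rule that gives each subject a single outcome. A fatal AE recorded as leading to discontinuation counts once, as the event. Say how an event dated at TEAE onset is matched to the recorded primary reason for stopping.
- **Cox model:** keep the cause-specific hazard ratio as planned.
- **7.2.1:** name the same estimator for the three by-reason discontinuation plots.
- **7.5.1.6:** no change, because it plans no cumulative incidence for this event.

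The cost is a few lines of SAP text and a standard SAS option (PROC LIFETEST with EVENTCODE). Reasons for discontinuation are already summarised, so no new data are needed. The downside is that these curves will differ in method from the other cumulative-incidence displays and need a footnote saying so.
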